## SYNOPSIS

### Study Title

A randomized, parallel-group (autogenous ex vivo produced oral mucosa equivalent (EVPOME) vs. palatal oral mucosa (POM)), safety and efficacy study in subjects requiring additional keratinized oral mucosa for dental rehabilitation or around erupted teeth to restore periodontal health.

### Objectives

The study objective is to assess the safety and efficacy for use of human EVPOME for soft tissue intraoral grafting procedures compared to the “gold standard” palatal oral mucosa (POM) graft.

### Design and Outcomes

This is a randomized, parallel-group phase II study to assess EVPOME vs. POM to determine differences in the primary efficacy measure of increased keratinized mucosa; secondary measures of graft contracture and Wound Healing Index; and ancillary outcome measures of tissue perfusion measured graft color and laser Doppler flowmetry, and postoperative pain.

Primary outcome measure: Clinical increase in zone (width) of keratinized mucosa (KM). For edentulous sites, KM width will be measured by determining the distance from the crest of the edentulous ridge to the mucogingival line to the nearest millimeter with a Castroviejo caliper. For patients with an existing implant, KM width will be measured from the implant mucosal margin to the mucogingival line. The amount of attached gingival tissue (keratinized) will be evaluated using a calibrated periodontal probe measured to nearest 0.5mm.

Secondary outcome measures: Graft contracture will be measured in mesio-distal and corono-apical directions. Post-surgical measurements of the graft site will be taken at visits 5, 6, 7, and 8, and will be compared to the original graft size to assess percentage of graft contracture. Wound Healing Index (WHI) will be recorded after surgery using the following criteria:

- Score 1= uneventful healing with no gingival edema, erythema, suppuration, patient discomfort, or flap dehiscence
- Score 2 = uneventful healing with slight gingival edema, erythema, patient discomfort, or flap dehiscence, but no suppuration
- Score 3 = poor wound healing with significant gingival edema, erythema, patient discomfort, flap dehiscence, or any suppuration

Ancillary outcome measures: Laser Doppler flowmetry (LDF) measurements will be used

to assess graft blood flow (tissue perfusion of the grafts).

Graft color is correlated to vascular perfusion and thus can give us an indication of graft vascularity. Finger pressure will be applied in the center of the graft for 15 seconds and/or until tissue blanching. The pressure will then be released and the time for the tissue to return to its previous color will be recorded. If the tissue returns to its previous color within 15 seconds, this will be recorded as positive graft vascularity. If not, then it will be recorded as negative graft vascularity.

Overall postoperative pain will be assessed via a visual analog scale (VAS).

### Interventions and Duration

The outcomes data in patients treated with experimental EVPOME soft tissue intraoral grafting procedure will be compared to the outcomes in patients treated with POM, which is the standard of care procedure. Those randomized to the experimental group will undergo a small 6mm palatal punch biopsy. Keratinocytes extracted from the punch biopsy will be harvested and expanded *in vitro* then seeded onto the AlloPatch®. This process will take approximately 30 days depending on the period of time needed for cell amplification. EVPOME or POM will then be grafted onto the oral defect and secured with absorbable sutures. At Week 4, after grafting, a 2 mm punch biopsy will be taken to assess degree and maturity of keratinization and microvessel ingrowth.

Throughout the duration of the study, the subject will return for subsequent study visits to assess oral health and graft healing, contracture, and revascularization. The subjects will attend 7-8 scheduled study visits, one of which will be the grafting procedure, over a period of approximately 30 weeks. The post-operative follow-up period will include 5 study visits over approximately 24 weeks.

### Sample Size and Population

Sixty (60) subjects, thirty (30) subjects per treatment group, will be randomized to receive either the experimental treatment, EVPOME (Group 1), or standard of care, the palatal oral mucosa (POM) graft (Group 2). The study population will include non-smoking adults (ages 18 and older) in need of additional keratinized oral mucosa.

Subjects will be recruited from UMHS through clinic referrals and the UMHS clinical research web portal for UMClinicalStudies as well as the University of Michigan (U-M) School of Dentistry, and their graduate periodontics clinic. Subjects may be also be recruited via Clinicaltrials.gov.

## 1. STUDY OBJECTIVES

### 1.1 Primary Objective

To assess the safety and efficacy for use of human EVPOME for soft tissue intraoral grafting procedures compared to the “gold standard” palatal oral mucosa (POM) graft.

#### **Short-term impact:**

Regeneration of oral mucosal tissue has not been previously addressed in craniomaxillofacial soft tissue injuries. At present, there are no successful means of repairing or regenerating soft tissue structures that contain mucosa, such as oral mucosa, or facial tissue units with a muco-cutaneous (M/C) junction, such as the lip. Damage to these tissues may occur in active military personnel during military operations. The lack of sufficient mucosal tissue is a reconstructive challenge that limits the ability of surgeons to reconstruct the oral cavity and other functional facial units that contain an M/C junction, such as the lips. This reconstructive challenge is frequently encountered by surgeons who treat traumatic avulsion injuries. Tissue engineering/regenerative medicine (TE/RM) offers a unique opportunity to address such reconstructive challenges using an innovative application of our proven technology and the surgical procedures proposed in this application.

The *in vitro* development of a tissue-engineered human oral mucosa is important because it can assist in intraoral reconstruction of the oral cavity and other mucosal structures such as the lips, eyelid, and anterior nares. For example, in the lip, the oral mucosa extends onto the vermilion border to unite with the skin of the face to form an M/C junction and is similar to the mucosa seen in the nasal cavity and inner aspect of the eyelid and the conjunctiva. Skin equivalents have been developed for treatment of burns and chronic wounds. The development of an *ex vivo* produced oral mucosal equivalent (EVPOME) has lagged behind that developed for skin.

An impediment to clinical use of TE/RM has been the lack of clinical validation trials and development activities. These are necessary to accelerate the transition of medical technologies, clinical practice guidelines, and standards of care into clinical capabilities. The clinical trials must be relevant to the definitive and rehabilitative care for patients. Of special concern are the injured war fighters who must be returned to readiness in terms of duty performance and quality of life. We will address the rehabilitative-reconstructive deficiency of contemporary options to regenerate mucosa and M/C junction. The proposed clinical trial is a compelling step to a solution.

#### **Long-term impact and potential to change the standard of care:**

The ultimate source of the cells to develop the soft tissue constructs will come from the patient, thus making the construct autochthonous (self to self). There are several advantages of using a TE/RM approach to reconstruct craniofacial soft tissue injuries:

- 1) Reduced donor site morbidity (we do not have to use extremities as a tissue source thus shortening the rehabilitation phase);
- 2) Improved restoration of function (rate and degree);
- 3) Reduced frequency of surgeries and operating room time;
- 4) Enhanced quality and shape of the regenerated soft tissue; and
- 5) Decreased hospital personnel and cost.

**Potential to change the standard of care:**

The results from this study will provide information to plan a Phase III clinical trial which will utilize larger wounds. A Phase III study will simulate the repair of major maxillofacial soft tissue intraoral defects that are in need of keratinized oral mucosa and will include medically compromised patients. The ability to assess keratinocyte metabolic activity and function prior to grafting is an essential component to assure a higher graft success rate. The potential phase III clinical trial could shift paradigms in surgical reconstruction of avulsion injuries to soft tissues containing oral mucosa and functional facial units with a mucocutaneous border (lips). The trial will also assist in the validation of a method to fabricate composite soft tissue grafts that will supplant facial transplants that require lifetime immunosuppression.

This Phase II clinical trial will be the first step in a paradigm shift on how soft tissue reconstruction of traumatic avulsion injuries of functional facial units will eventually be treated.

## 2. BACKGROUND

### 2.1 Rationale

The need for improved technology for craniofacial reconstruction is extremely relevant to military patients considering the high prevalence of combat-related craniomaxillofacial (CMF) injuries. A recent study analyzed the Joint Theatre Trauma Registry database for maxillofacial battle-injuries (BI) experienced by U.S. soldiers in the Iraq/Afghanistan conflicts to describe the type, distribution, and mechanism of injury. The study identified 7,770 BI of which 26% had maxillofacial involvement. The primary mechanism of injury was due to explosive devices (84%).

The study concluded that Maxillofacial BI account for a disproportionate number of injuries observed in Iraq and Afghanistan compared to previous American wars. Thus, the focus of this study on soft tissue reconstruction is especially pertinent given the significant number of soft tissue penetration injuries from explosive devices.

Craniofacial soft tissue defects that result from explosive munitions wounds to unprotected regions of the body, such as the face, present unique requirements among tissue engineering applications. Furthermore, the nature of explosive penetration wounds often creates extremely complex geometric and avulsion defects. The EVPOME technology will address these evocative challenges.

We can now fabricate human tissue-engineered oral mucosa (EVPOME). By conducting this planned Phase II clinical trial, we will improve and advance therapeutic technology for soft tissue craniofacial reconstruction which is profoundly relevant to military patients. The knowledge gained from this study will lead to a Phase III clinical trial where we will focus on larger maxillofacial intraoral defects that need oral mucosa.

This project will also be synergistic with another Department of Defense (DoD) project recently awarded, “Tissue Engineering Lips for Use in Repair of CMF Soft Tissue Injuries.” One of the most difficult areas of the face to reconstruct after avulsion is the lips because they represent a composite tissue of mucosa, skin, and muscles. Significant loss of these structures is an obvious functional and esthetic concern because the neuromuscular control of normal lip structures is required for everyday activities of eating, drinking, talking, and social gestures. Avulsion of the lips is a survivable injury, but without functional lip reconstruction, life for these injured service members is burdened by drooling, food spillage while eating, unintelligible speech, and social rejection. Success of this study will enable movement of the “lip” project into the clinical arena sooner, as the methodology and protocols being used are quite similar. The success of the lip repair/reconstruction project is predicated by the ability to bring our tissue-engineered human oral mucosa into the clinical arena. Thus, this Phase II clinical trial will be a precursor for the successful implementation of a clinical trial for soft tissue reconstruction of the lips which incorporates the use of oral mucosa.

## 2.2 Supporting Data

A previous Phase I clinical trial demonstrated the safety and efficacy of EVPOME to increase keratinized gingival tissue without adverse events or local complications. This study achieved its main objectives and informed the design of the prospective clinical trial described here. For the phase I clinical trial, the researchers did not receive approval to have a control group (i.e., AlloDerm® without cultured primary oral keratinocytes), since the study was done to determine safety of the EVPOME and not efficacy. Thus, no post-operative biopsy specimens were obtained to assess vascularization of the tissue or persistence of the grafted cultured cells. Also note that while the previous study was performed using AlloDerm® as the scaffold upon which the EVPOME is constructed, this study will use AlloPatch® which is very similar to AlloDerm®. AlloPatch® must be used in this study because AlloDerm® is no longer available.

Previous studies showed that the grafted EVPOMEs had a deeper red hue than AlloDerm® grafts at post-operative day 6. This observation suggests that the grafted EVPOMEs revascularized faster than AlloDerm® grafts. In addition, there was histologic and immunohistochemical documentation of microvessel ingrowth into the underlying dermal component, AlloDerm®, of the EVPOME in a study of severe combined immunodeficient mice. It can therefore be reasonably stated that the grafted EVPOME had undergone revascularization by postoperative days 7 to 14.

The previously mentioned completed Phase I clinical trial was distinctive from other case studies using tissue-engineered products because it was conducted under our CBER/FDA-approved, investigator-initiated IND 10118. The IND required specific and rigorous cell testing and monitoring of the biologic product. Glucose consumption was selected as the functional test because it was considered a good indicator of the number of viable cells present on the EVPOME. Glucose consumption could detect cellular variations within EVPOME grafts, even in material from the same individual. As such, this functional test addresses the quality assurance/control and the release criterion mandated by CBER/FDA.

Overall, the cell culture protocols used in this clinical trial proved to be acceptable, since all EVPOMEs were successfully grafted into subjects with no signs of morbidity and/or contamination. The release criterion of glucose consumption correlated well with histologic examination of the EVPOME. Results showed a direct correlation between glucose consumption and the presence of a well-stratified oral mucosa epithelial layer. Therefore, the glucose consumption testing for this protocol will be similar to that of the earlier phase I study under IND 10118.

### 3. STUDY DESIGN

This safety and efficacy study will be a single site, randomized, parallel-group autogenous ex vivo produced oral mucosa equivalent (EVPOME) vs. the “gold standard” palatal oral mucosa (POM), in subjects requiring additional keratinized oral mucosa.

A total of sixty subjects will be randomized in a 1:1 ratio to autogeneous EVPOME vs. POM. If randomized to EVPOME, the subjects will be scheduled for a harvest biopsy (Visit 2 procedure). If randomized to the POM group, the subjects will be scheduled for the graft (Visit 3 procedure). See Table 1(Section 6.1) for the Schedule of Evaluations. Subjects will be non-smoking adults (18 years and older) needing increased keratinized oral mucosa.

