## 6.2 Evaluation Schedule

### 6.2.1 **Visit 1 Screening**

Subjects will be recruited through the Patient Admitting and Emergency Services (PAES) clinic in the U-M School of Dentistry in conjunction with MCOHR. All new patients are routed through PAES and assigned to specialty or undergraduate clinics. Most patients do not return to the PAES clinic, so we are not likely to have redundancy. PAES had 13,100 visits in 2003. It is estimated that 40% of the western population is missing 1 or more teeth (50% to be restored with implants for our purposes). Approximately 1/3 of them are in need of soft tissue oral mucosa grafts which is a very common procedure. This will give us a population from which to draw approximately 865 new patients per year. Of this group we need to recruit 60 subjects over two years from a potential pool of 1,730 patients. With an estimated enrollment of 1 out of 4 screened patients, we should have a pool of over 400 patients per year from which to select 30 subjects. Subjects will be recruited by full-time faculty members in the Department of Periodontics at the U-M School of Dentistry.

Informed consent will be obtained from each subject before any study-related procedures are performed. Screening and consenting procedures will be performed by the study staff on site at the clinic.

During the consenting process, the study staff will allow time for the subject to review the Informed Consent Form, ask questions, and make an informed decision (i.e. allow the subject to discuss with family etc.).

If the subject is willing and able to consent, the study staff will perform the study-specific procedures and evaluations to determine eligibility. Determination of eligibility will include review of subject-reported medical and dental history, an oral examination, and x-rays, if necessary. Subject weight will also be collected.

Medical and dental history will be questioned to determine any history of special conditions that may affect the subject during the study and its associated procedures. Potential study contraindications may include history of heart disease, relevant allergies, or the use of medications such as blood thinners. Concomitant medications will be updated throughout the trial. A visual analog scale of pain will be taken at this time for both group I and II,

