## 9. STATISTICAL CONSIDERATIONS

### 9.1 General Design Issues

This is a randomized, parallel-group (autogenous *ex vivo* produced oral mucosa equivalent (EVPOME) vs. palatal oral mucosa (POM)) safety and efficacy study in subjects requiring additional keratinized oral mucosa for dental rehabilitation. The primary hypothesis is that EVPOME is an equivalent intraoral grafting material when compared to POM in regards to keratinized tissue and graft contracture, but is superior to POM in regards to pain, color rendition, and microvessel infiltration.

The comparison will be done using primary efficacy measures of enhanced keratinization, and secondary measures of graft contracture and wound healing index, and ancillary measures of increased microvessel ingrowth. Clinical assessments will include postoperative pain. Intraoral photographs will be done at screening and at biopsy, 2, 4, 8, and 24 weeks after intra-oral grafting. Tissue biopsy will be conducted at week 4 and laser Doppler flowmetry at weeks 2, 4, 8, and 24. Primary assessment time will be at week 4, and final assessments for all subjects will be at week 24.

Subjects will be screened until we have the necessary 60 enrolled. It is likely there will be 4 screened subjects to 1 enrolled subject. All subjects will undergo informed consent prior to any screening procedures. It is expected that it will take 2.5 years to successfully enroll 60 patients. Subjects will be recruited through the Patient Admitting and Emergency Services (PAES) clinic in the U-M School of Dentistry in conjunction with MCOHR. All new patients are routed through PAES and assigned to specialty or

undergraduate clinics. Most patients do not return to the PAES clinic, so we are not likely to have redundancy. PAES had 13,100 visits in 2003. It is estimated that 40% of the western population is missing 1 or more teeth (50% to be restored with implants for our purposes). Approximately 1/3 of them are in need of soft tissue oral mucosa grafts which is a very common procedure. This will give us a population from which to draw approximately 865 new patients per year. Of this group we need to recruit 60 subjects over two years from a potential pool of 1,730 patients. With an estimated enrollment of 1 out of 4 screened patients, we should have a pool of over 400 patients per year from which to select 30 subjects. Subjects will be recruited by full-time faculty members in the Department of Periodontics at the U-M School of Dentistry.

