### 9.3 Sample Size and Accrual

We propose to have 60 subjects to give clinical and histological endpoints of interest at the primary assessment time of 4 weeks post graft. We expect no more than 6 subjects to potentially drop out of the study before providing Week 4 data, and thus will enroll 66 patients in total. With an estimated enrollment of 1 out of 5 screened patients, we expect to have a pool of over 330 patients over two years from which to select 66 subjects (33 subjects per group over two years) that will be randomized equally to one of the two groups - EVPOME and POM grafts. The randomization list will be prepared electronically in advance by the biostatistician and transferred to the MICHR statistics group for incorporation into the TATUM system. Randomization will be stratified by smoking status.

The primary clinical endpoint is the degrees of keratinized tissue. Secondary outcomes are contracture and wound healing index. Ancillary endpoints include the presence or absence of a continuous epithelial layer, the degree of vascular ingrowth, the LDF measurement of gingival blood flow. The main aim is to show that EVPOME treatment give comparable clinical and histological results when compared with POM treatment. It is also expected that the EVPOME will cause less patient discomfort and pain, and have a better color rendition to the surrounding tissue than the POM. Hence, we expect EVPOME to show better outcomes for pain, color rendition, and microvessel infiltration than POM, while showing comparable outcomes on primary endpoints of keratinized tissue and graft contracture or histological endpoints compared with POM. Sample size is calculated to show near equivalence of the two groups for primary and secondary outcomes. Sample size calculation and power consideration are provided following the data analytic plan described for each outcome.

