## 9.5 Data Analyses

The main aim of the study is to determine by quantitative outcome measures that EVPOME will function as well as POM in terms of increased epithelialized tissue, decreased contracture, and increased microvessel infiltration. It is also expected that the EVPOME will have a closer adaptation in color rendition to the surrounding tissue. Our primary comparisons will be based on the observations at four weeks post-graft.

**AIM 1 - Keratinized Tissue:** Primary comparison will be based on week 4 assessment using an equivalence test of means. Background data on measurements of keratinized tissue for POM (standard of care) gave a mean measurement of 3.70 mm with an SD of 0.65 mm. The mean and SD were relatively constant over the follow up period from 3 to 12 months. If, in this study, both EVPOME and POM give comparable results, the distribution of the mean difference in keratinized tissue with 30 subjects in each arm will be approximately normal with a mean of 0 and standard error of 0.17, and a 95% confidence interval for the true mean difference between the two procedures will have a margin of error of about 0.33 mm. This confidence interval will exclude a value for the mean difference of 0.55mm or larger with probability at least 80%. Therefore sample size will be adequate to show near equivalence of the two treatments if the degree of keratinized tissue measurement of EVPOME is within  $\pm 0.55$ mm of POM. Statistical power will be even larger if non-inferiority of EVPOME to POM is desired, where true increase in keratinized zone in EVPOME group is no less than 0.55 mm compared with the increase of zone of keratinized tissue in POM.

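### The plan randomizes 60 subjects in some sections and 66 in Section 9.3; with 60 randomized and the planned six losses, primary equivalence power is about 75%, below the stated 80%

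*Combined protocol and SAP*

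**What the plan says.** Four places set the total at 60.

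- Synopsis, Sample Size and Population: "Sixty (60) subjects, thirty (30) subjects per treatment group, will be randomized".
- Section 3, Study Design: "A total of sixty subjects will be randomized in a 1:1 ratio".
- Section 6.2.1, Visit 1 Screening: "Of this group we need to recruit 60 subjects over two years".
- Section 9.1, General Design Issues: "Subjects will be screened until we have the necessary 60 enrolled".

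Section 9.3, Sample Size and Accrual, gives 60 a different meaning: "We propose to have 60 subjects to give clinical and histological endpoints of interest at the primary assessment time of 4 weeks post graft". It expects at most six subjects to be lost "before providing Week 4 data, and thus will enroll 66 patients in total". It then describes a pool from which to "select 66 subjects (33 subjects per group over two years) that will be randomized equally to one of the two groups".

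Section 9.5, Aim 1, plans an equivalence test of means at Week 4. With 30 subjects in each arm it gives a standard error of 0.17 mm and a 95% margin of error of about 0.33 mm. It concludes: "This confidence interval will exclude a value for the mean difference of 0.55mm or larger with probability at least 80" percent. Aim 2 makes the matching claim for contracture, with an SD of 13%, a difference of 11% and the same 30 per arm.

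**The concern.** Saying that 60 is the evaluable count and 66 the randomized count does not remove the conflict, because the synopsis and Section 3 also speak of subjects randomized. A site that follows Section 3 and the screening rule in Section 9.1 would stop at 60. The plan's own loss allowance would then leave 54 subjects with Week 4 data, or 27 per arm if losses are even. The power statements in Section 9.5 were written for 30 per arm, so the primary claim and the contracture claim would both miss their stated 80%. Once accrual has closed at 60, the shortfall cannot be made good.

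Losses between randomization and Week 4 are possible in this design. Randomization takes place at Visit 1. EVPOME subjects then wait through a harvest biopsy and a culture period of roughly 30 days. Section 6.2.3 describes an exit that only that arm has: fabrication fails, and the subject declines a second biopsy and withdraws.

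**Working it through.** **Inputs (Section 9.5, Aim 1):** SD 0.65 mm; margin ±0.55 mm; true difference 0; 95% two-sided confidence interval, so each one-sided test is at 0.025. From Section 9.3: 60 evaluable, at most 6 lost, 66 enrolled.

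**Formulas (normal approximation, as in the plan):**

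- SE = SD × √(1/n₁ + 1/n₂)
- Power = 2Φ(margin/SE − 1.96) − 1

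**Reproducing the plan's figures, 30 per arm**

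- SE = 0.65 × √(2/30) = 0.168 mm (plan: 0.17)
- Margin of error = 1.96 × 0.168 = 0.329 mm (plan: 0.33)
- Power = 2Φ(0.55/0.1678 − 1.96) − 1 = 81.2% (plan: at least 80%)

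All three agree, so this is the plan's method. The enrollment inflation also agrees: 60/(1 − 6/66) = 66.

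**60 randomized, six lost, 27 per arm**

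- SE = 0.65 × √(2/27) = 0.177 mm
- Margin of error = 1.96 × 0.177 = 0.347 mm
- Power = 2Φ(0.55/0.1769 − 1.96) − 1 = 74.9%

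**Power by number of losses when 60 are randomized**

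| Lost | Evaluable per arm | Power |
|---|---|---|
| 0 | 30 and 30 | 81.2% |
| 2 | 29 and 29 | 79.3% |
| 4 | 28 and 28 | 77.2% |
| 6 | 27 and 27 | 74.9% |
| 6, all in one arm | 24 and 30 | 74.1% |

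Thirty per arm is the smallest equal allocation that reaches 80%. If the loss rate of 6/66 = 9.1% is applied to 60 in place of a flat six, about 54.5 subjects remain (27.3 per arm) and power is 75.6%.

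**Contracture.** The margin-to-SD ratio is the same (11/13 = 0.55/0.65 = 0.846), so power again falls from 81.2% to 74.9%. The SE goes from 3.36 to 3.54 percentage points.

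**Margin that would keep 80% at 27 per arm.** Margin = (1.960 + 1.282) × SE. This gives 3.242 × 0.1769 = 0.57 mm for keratinized mucosa width and 3.242 × 3.538 = 11.5 points for contracture.

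**Sensitivity to the t distribution.** A t-based equivalence test gives 79.3% at 30 per arm, 72.5% at 27 per arm and 71.6% at 24 versus 30. This is not the plan's calculation, but it shows how little slack there is.

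**The case against.** The strongest reply is that nothing in Section 9.5 is miscalculated. Its 80% is conditional on 30 subjects in each arm and is correct there. Section 9.3, the section devoted to sample size, also separates evaluable from enrolled subjects and makes the right allowance. On this view other sections simply fail to carry the number through. That is so, and it identifies the likely source of the error, but it does not tell the site when to stop enrolling.

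Second, six is a ceiling. With fewer losses the shortfall is smaller, and with none there is no shortfall. This stands: 75% is the figure at maximum planned loss and is not a forecast. Section 6.2.3 also reports that no Phase I procedure was aborted for failing release criteria, so the scenario with all six losses in the EVPOME arm is only an illustration.

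Third, the result depends on the 95% interval. A 90% interval equivalence test would have 85.7% power at 27 per arm, and one-sided non-inferiority at 0.025 would have 87.5%. Aim 1 mentions non-inferiority as a possible reading. It names equivalence as the primary comparison, however, and rests its 80% on a 95% interval.

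Finally, the practical loss is modest: about six points of power in a phase II trial, or 0.02 mm on the margin, when width is read to the nearest millimeter. That bears on how serious the power loss is. It does not resolve the contradiction over how many subjects are randomized.

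**Conclusion.** The concern holds. The plan gives two incompatible totals for the number randomized. Section 9.5's power claims fit only the larger one once the planned losses occur. If the trial stops at 60, power for keratinized mucosa width and for contracture falls below 80% once each arm has lost one subject, and reaches about 75% (74.9%) at the plan's limit of six losses.

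This rests on the plan's own SDs and margins, a true difference of zero, a 95% confidence interval, the normal approximation and losses spread evenly over the arms. If 66 are randomized and six are lost, the stated figures stand.

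**What to change.** Choose one total and state it everywhere, separating the number randomized from the number evaluable at Week 4.

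- **Option A, Section 9.3's own figures.** Put 66 randomized (33 per arm), to give 60 evaluable at Week 4, into the synopsis and Sections 3, 6.2.1 and 9.1. Section 9.5 then needs no change.
- **Option B, if 60 is the approved total.** Correct Section 9.3 to 60 and restate Section 9.5 for 27 evaluable per arm. That means about 75% power at 0.55 mm and at 11 points, or 80% power at about 0.57 mm and 11.5 points. A wider margin would need its own clinical justification. The remaining precision and power statements in Section 9.5, also based on 30 per group, should be restated too.

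Option A adds six subjects to the total in the synopsis and Section 3, a number Section 9.3 already plans for. Option B costs only a less favorable power statement. Both change the protocol text, so both need the IRB review that Section 11.1 requires for modifications. The change should be made before enrollment reaches 60.
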